9.2.4 Maintenance of Wakefulness Test (MWT)

The MWT is an evaluation used as a quantitative polysomnographic (PSG) measurement of daytime wakefulness/somnolence during soporific circumstances. During each trial, subjects will sit quietly on the bed with both back and head supported by a pillow, and subjects will be asked to look directly

Sponsor BenevolentAI Bio

Project Code ... BB-2001-201b

ahead and try to stay awake as long as they can. If they fall asleep, they will be woken up after 90 seconds and the trial will end if the subjects do not fall asleep within 40 minutes. Start and stop times for each trial, sleep latency, total sleep time, stages of sleep achieved for each trial, and the mean sleep latency (the arithmetic mean in minutes of the four trials) will be recorded, considering sleep latency as the time from lights out until the first epoch of greater than 15 sec of cumulative sleep in a 30-sec epoch of either 3 consecutive epochs of stage 1 sleep, or one epoch of any other stage of sleep. Absolute change in the MWT from baseline to the end of the 6-week treatment period. Mean MWT sleep latency scores will be calculated for each of the 4 sleep trials. Also the total sleep latency scores average will be calculated for each patient according to the 4 round MWT sleep latency scores. If some of the latency scores are missing the total sleep latency score average will be calculated just considering the available data and dividing it by the number of non-missing tests. Sleep latency scores will be analysed and presented in minutes.

9.2.5 Polysomnography

Mean absolute change in the polysomnography parameters (as defined below) from baseline to the end of the 6-week treatment period:

Sleep Stage Parameters:

Total Recording Time (TRT) is defined as the time in minutes from “lights out” to “lights on”. Total Sleep Time (TST) is the total time in minutes asleep after sleep onset. To determine the how well the patient slept, the Sleep Efficiency (SE) is calculated by dividing the TST by the TRT and multiplying by 100. Sleep studies are recorded on 30 second “epochs”. Sleep onset is defined as the first epoch scored as any stage other than stage W. Sleep Latency (SL) is the time from “lights out” to the sleep onset. Latencies to sleep stages are determined from sleep onset to the first epoch of that sleep stage. Wake after Sleep Onset (WASO) is the time awake after sleep onset until “lights on”. To determine the percentage time spent in each of the sleep stages during the sleep study, the total minutes of the sleep stage is divided by the TST and multiplied by 100.

Sleep information:

Percentage of TST Ni (for i=1 to 3) is calculated as a percentage: $(\text{Minutes Ni} / \text{TST} * 100)$

Percentage of TST REM is calculated as a percentage: $(\text{Minutes REM} / \text{TST} * 100)$

Clinical Event Parameters:

Event (or arousal) index will be calculated as the number of events (arousal number) divided by TST and multiplied by 60 (events per hour).

Events Index= $(\text{Events}/\text{TST}) * 60$.

Arousal Index= $(\text{Arousal number}/\text{TST}) * 60$.

Index will be calculated for the events and arousal detailed below:

- Apnoea
- Hypopnea
- Apnoea + Hypopnea
- Limb Movement

Sponsor BenevolentAI Bio

Project Code ... BB-2001-201b

- Periodic Limb Movement
- Arousals index
- Spontaneous Arousals index
- Apnoea Arousals index
- Hypopnea Arousals index
- LM Arousals index
- PLM Arousals index
- Desaturation Arousals index
- Snore Arousals index
- Respiratory Arousals index
- Respiratory Effort Related Arousal (RERA) index
- User Defined Arousals index
- Total Arousals index

9.2.6 Unified Parkinson's disease Rating Scale Part III (UPDRS Part III)

UPDRS III mean absolute change from baseline to the end of the 6-week treatment will be defined as Total UPDRS III score at visit 3 – Baseline UPDRS III score. Part III contains 33 scores based on 18 items, several with right, left or other body distribution scores.

When UPDRS is missing in some scheduled post-baseline visit (visit 2 or visit 3) any other UPDRS value measured in whether an unscheduled visit or in the early termination visit will be considered according to the re-allocation windows rules presented in the section 4.1. The same analysis will be repeated for the 2-week evaluation. If more than 75% of the scores are missing then the total motor examination score will not be calculated and considered as not evaluable. The same rule will be applied for the subscales calculation. This threshold could be re-evaluated in advance to the data base lock according to the missingness rate in the data.

9.2.7 Hamilton Rating Scale for Depression (HAM-D)

Mean absolute change in the depression HAM-D score (as defined below) from baseline to the end of the 2-week and 6-week treatment period and safety follow-up (defined as 28 days \pm 2 after Visit 3 or early termination visit). Although the HAM-D form lists 21 items, the scoring is based on the first 17. For the total sum, 8 items are scored on a 5-point scale, ranging from 0 (not present) to 4 (severe), and the remaining 9 are scored from 0 to 2. HAM-D total score is calculated as the sum of the first 17 items. This threshold could be re-evaluated in advance to the data base lock according to the missingness rate in the data. If more than 75% of the scores are missing then the total motor examination score will not be calculated and considered as not evaluable. The same rule will be applied for the subscales calculation.

9.2.8 Montreal Cognitive Assessment (MoCA)

Mean absolute change in the MoCA total score as defined below from screening to the end of the 6-week treatment period.

It assesses different cognitive domains: attention and concentration, executive functions, memory, language, visuoconstructional skills, conceptual thinking, calculations, and orientation. Sum all sub scores listed on the right-hand side. Add one point for an individual who has 12 years or fewer of

Sponsor BenevolentAI Bio

Project Code ... BB-2001-201b

formal education, for a possible maximum of 30 points. The total possible score is 30 points; a score of 26 or above is considered normal.

9.2.9 Fatigue Severity Scale (FSS)

Mean absolute change in the Fatigue Severity Scale, as defined below.

The FSS is a self-administered questionnaire with 9 items investigating the severity of fatigue in different situations during the past week. There are 9 items ranging from 1 to 7, where 1 indicates strong disagreement and 7 strong agreement, and the final score is calculated as the mean value of the 9 items. If more than 75% of the items are missing then the FSS total score will not be calculated as will be considered as not evaluable. This threshold could be re-evaluated in advance to the data base lock according to the missingness rate in the data

9.2.10 Berlin Questionnaire (BQ)

Percentage of patients with BQ high risk (as defined below) at week 2 and 6 will be determined.

This questionnaire consists of 3 categories (questions 2 to 6 about snoring [category 1], questions 7 to 9 about daytime somnolence [category 2], and question 10 about hypertension and BMI [category 3]) and the risk is based on the responses to individual items and overall scores in the symptom categories.

Categories and Scoring:

Category 1: items 2, 3, 4, 5 and 6;

Item 1: if 'Yes', assign **1 point**

Item 2: if 'c' or 'd' is the response, assign **1 point**

Item 3: if 'a' or 'b' is the response, assign **1 point**

Item 4: if 'a' is the response, assign **1 point**

Item 5: if 'a' or 'b' is the response, assign **2 points**

Add points. *Category 1 is positive if the total score is 2 or more points.*

Category 2: items 7, 8, 9 (item 9b should be noted separately).

Item 7: if 'a' or 'b' is the response, assign **1 point**

Item 8: if 'a' or 'b' is the response, assign **1 point**

Item 9: if 'a' is the response, assign **1 point**

Add points. *Category 2 is positive if the total score is 2 or more points.*

Category 3 is positive if the answer to item 10 is 'Yes' or if the BMI of the patient is greater than 30kg/m². (*BMI is defined as weight (kg) divided by height (m) squared, i.e., kg/m²*).

High Risk: if there are 2 or more categories where the score is positive.

Low Risk: if there is only 1 or no categories where the score is positive.

Sponsor BenevolentAI Bio

Project Code ... BB-2001-201b

9.3 Exploratory Efficacy Endpoints

- Free living activity assessed by means of wrist-worn actigraphy.

9.4 Analysis sets Analysed for Efficacy

Primary Analysis, and sensitivity analysis as described above will be based in the ITT Population. In the MCP-Mod sensitivity analysis, only patients in the ITT with ESS evaluations at week 6 will be considered. Primary analysis will be repeated in the Per Protocol Population also which will be considered as a sensitivity analysis.

10 STATISTICAL METHODOLOGY FOR EFFICACY ENDPOINTS

10.1 Primary Efficacy Analysis

ESS mean absolute change from baseline to the end of the 6-week treatment period will be analysed with an ANCOVA model, with the baseline ESS as a covariate, region and treatment as a factor. Least-squared (LS) absolute mean changes will be presented by treatment group along with their associated 95% CIs and 2sided p-values; these data will then provide estimated for the within arm change from baseline. The difference between each of the 3 dose arms and the placebo arms in Least-squared (LS) absolute mean changes will also be presented together with the corresponding 95% confidence interval and 2-sided p-value. These paired comparisons will be performed without any multiplicity adjustment. Also, the 4 degrees of freedom (DF) associated with the overall F-test for differences between the treatment arms will be decomposed using Type I sums of squares into three orthogonal single DF contrasts to estimate the linear, quadratic and cubic components of any potential dose response. Baseline data will be imputed with the baseline ESS average. Multiple Imputation Jumping to Reference method will be used to impute post-baseline data (see section 10.4.2 for further reference).

10.1.1 Sensitivity analyses missing reductions imputed to 0:

Same primary analysis will be repeated imputing post-baseline missing ESS evaluations to baseline data that is reduction equal to 0.

10.1.2 Sensitivity analyses MMRM Model:

A mixed-effect model with repeated measures (MMRM) approach will be used, under the missing at random framework carried out using an adequate contrast at Week 2 or Week 6, accordingly. The model will include fixed categorical effects of treatment group, region, visit and treatment-by-visit interaction as well as the continuous fixed covariates of mean baseline ESS. This MMRM model will be run with an unstructured correlation matrix to model the within subject errors. In this case missing values will not be imputed, since (MMRM) is handling missing data through the Maximum Likelihood estimation method.

Unstructured covariance matrix is assumed to explain within subject covariance in MMRM method in protecting the type I error rates. In the event if the assumption of unstructured covariance (UN) matrix results in non-convergence of the model, only then the following covariance structures will be considered in the order mentioned below.

The order of covariance structure to be considered is:

1. Compound Symmetry (CS)

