# 8.6.6 Method of Assigning Subjects to Treatment Groups

A computer-generated randomisation scheme by region will be provided by Nuvisan according to Sponsor specification.

Subjects will be randomized in order to have 200 completed subjects. At the end of the baseline period on day -1, all subjects fulfilling the inclusion and exclusion criteria will be randomly allocated to one of the 4 treatment groups at a ratio of 1:1:1:1.

Treatment group 1: Bavisant 0.5 mg tablets
Treatment group 2: Bavisant 1.0 mg tablets
Treatment group 3: Bavisant 3.0 mg tablets

Treatment group 4: Placebo tablets

The randomisation will be stratified by region and by the polysomnography and the MWT assessment which will be performed to a subset of subjects (around 50%). The information on whether the subject will do the polysomnography and the MWT assessment will be collected first and the randomisation will be performed based on this information. A first block of medication according to the randomisation scheme created will be provided to each site. Upon completion of the first block of medication, the site should request a new supply of medication. In this case, if the subject will perform both the polysomnography and the MWT assessment, the randomisation number being provided will be selected as the first available from the bottom of the randomisation list; otherwise the subject will receive the maximum available subject number. With this method (also known as down-up / up-down) the randomisation can be stratified by polysomnography/MWT assessment with one single randomisation list and so guaranteeing a similar 1:1:1:1 distribution between strata.

The randomisation number will consist of a 3-digit number which will be linked to the respective electronic case report form (eCRF) number.

At the end of the baseline period, subjects will be randomly allocated to 1 of the 4 treatment groups and given the IMP with the next available randomisation number in either ascending or descending sequence. The 3-digit randomisation number is printed on the labels of the study medication and will uniquely identify the IMP which is assigned to the subject. Each subject must

Amendment 04, Final Version 1.0 07/Nov/2018 Page 68 / 142

be given only the IMP carrying his or her randomisation number. The investigator will document the randomisation number in the eCRF and IMP accountability records.

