#### 11.1.3 Efficacy Analyses

# 11.1.4 Primary Efficacy Analyses

ESS mean absolute change from baseline to the end of the 6-week treatment period will be analysed with an ANCOVA model, with the baseline ESS as a covariate, region and treatment as a factor. Missing data in the 6-week ESS evaluation will be considered as a treatment failure, that is imputing the missing ESS reduction as 0. Least-squared (LS) absolute mean changes will be presented by treatment group together with their corresponding 95% confidence interval. Paired-comparisons will be performed without any multiplicity adjustment.

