#### 11.3. Randomisation Methods

Three regions will be defined: USA, Western Europe and Eastern Europe. Regionally randomization list will be performed to guarantee a ratio of 1:1:1:1 for the treatment groups by region. As the study intends on keeping that ratio of 1:1:1:1 both in the subjects who will perform a polysomnography/MWT assessment, and in subjects who will not do that assessment, a down-up/up-down strategy will be followed in order to simplify the stratified randomisation. This way, if the subject will perform both the polysomnography and the MWT assessment, he/she will receive the lowest available subject number at the respective study site; otherwise he/she will receive the maximum available subject number.

The randomisation schedule will be generated by Nuvisan CTS following a computer-generated randomisation scheme. The randomisation schedule will link sequential medication numbers to treatment codes. The medication numbers will be blocked to facilitate attainment of a homogeneous distribution of treatment groups.

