- (7) Pharmacogenomic blood sample to be obtained in subjects who specifically consented for this exploratory analysis.
- (8) The eye examination should be performed after the last treatment on Day 42 and before the follow up safety call.
- (9) Subjects will be instructed to have already taken their normally scheduled dose of anti-parkinsonian medication and their IMP prior to arriving at the study site in order to have their UPDRS Part III evaluated in ON (within approximately 1 to 3 hours after taking their levodopa dose). UPDRS in OFF will not be evaluated.
  - It is recommended that all assessment (s) establishing eligibility for the study to be performed first.
- (10) Any positive finding on the HAM-D, C-SSRS, or BPRS+ scales during the study will be referred to a trained mental health professional to be followed.
- (11) MWT and Polysomnography will be performed on a minimum of 50% of subjects (all recruited in sites with sleep units available)
- (12) Treatment will be taken from Day 1 to Day 42, both inclusive.

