2. The goal is to obtain the values c_1, c_2, c_3 and c_4 that maximize $(c'\mu)^2/(\sum c_i^2/n_i)$ where n_1, n_2, n_3 and n_4 are the sample sizes for placebo, 0.5, 1, and 3 mg/d respectively. To do so, the NLMIXED procedure will be applied on the above-mentioned one-record dataset to obtain the “maximum likelihood” parameters c_1, c_2, c_3 and c_4 using the following likelihood function:

$$ll = (\mu_1 * c_1 + \mu_2 * c_2 + \mu_3 * c_3 + \mu_4 * c_4) ** 2 / (c_1 ** 2 / n_1 + c_2 ** 2 / n_2 + c_3 ** 2 / n_3 + c_4 ** 2 / n_4);$$

There are infinite solutions to the above problem, so we will hold one coefficient to an arbitrary value (e.g. $c_1 = -10$).

3. Finally, the obtained coefficients will be normalized as follows (shown for c_1):

Sponsor BenevolentAI Bio
 Project Code ... BB-2001-201b

$$ncl=c1/(sqrt(c1**2 + c2**2 +c3**2 + c4**2));$$

For validation purposes, the obtained coefficients will be compared with the ones obtained using the dose-finding R package developed by te authors of MCP-Mod.

III. Dose Response Test

For each of the candidate models, dose-response association will be evaluated using the optimal coefficients identified in the previous step. These contrasts will be tested using the PROC GLIMMIX procedure at an one-sided alpha level of 0.025 and multiplicity adjusted p-values will be obtained through parametric resampling ESS mean absolute change from baseline to the end of the 6-week treatment period will be included in the model as dependent variable, dose as fixed factor and baseline ESS as covariate. SAS code like the code below will be used:

```
PROC GLIMMIX;
CLASS DOSES;
MODEL ESS = DOSES BASELINE /NOINT;
LSMEANS DOSES;
ESTIMATE "EMAX1"          DOSES &C11. &C12. &C13. &C14.,
        "EXPONENTIAL"    DOSES &C21. &C22. &C23. &C24.,
        "SIGMOID EMAX"    DOSES &C31. &C32. &C33. &C34.
        / UPPERTAILED ADJUST=SIMULATE (NSAMP=100000 SEED=1234) ;
RUN;
```

IV. Model Selection

The maximum contrast test method will be used to select the best model to be used in the Mod stage. The selected model will be fitted with PROC NLMIXED procedure using SAS code similar to the script below (shown for the Emax model only):

```
PROC NLMIXED;
BOUNDS S2>0, ED50 >0;
PARMS S2 BETA E0 EMAX ED50;
IF DOSE >0 THEN MEAN = E0+(EMAX*DOSE)/(ED50+DOSE) + BETA*BASELINE;
ELSE IF DOSE = 0 THEN MEAN= E0 + BETA*BASELINE;
MODEL ESS ~ NORMAL(MEAN, S2);
RUN;
```

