10.2 Secondary Efficacy Analysis

All secondary endpoints evaluated through a mean absolute change will follow a similar statistical analysis as for the primary variable (ANCOVA, considering baseline corresponding endpoint evaluation as covariate and treatment and region as fixed factors):

- Mean changes of ESS (up to 2-week treatment period)
- Mean relative change in the Epworth Sleepiness Scale (ESS) from baseline to the end of the 2-week and 6-week treatment periods (percentage of absolute decrease compared to baseline ESS).
- SCOPA-Sleep (up to 2-week and 6-week treatment period)
- PDSS-2 (2-week and 6-week)
- MWT (6-week)
- Polysomnography (6-week)
 - o Sleep Efficiency
 - o Percentage of TST REM
- UPDRS Part III (2-week and 6-week)
- Motor function assessed by the wrist worn device (6-week)
- HAM-D (2-week, 6-week and follow-up)
- MoCA (6-week), and FSS (6-week).
- Fatigue Severity scale (FSS)
- Polysomnography (6-week): Baseline index will not be considered in these Logistic models.
 - o Events Index (Increase in Events Index)
 - o Arousal Index (Increase in Arousal Index)

Categorical variables as detailed below will be analysed through fitted logistic regression model adjusted on baseline corresponding endpoint evaluation as a covariate and treatment and region as fixed factors. This model will estimate the adjusted Odds Ratio between treatment arms, its corresponding 95% and P-value.

- ESS clinical response, defined as ESS absolute decrease from baseline of at least 3.0 points, after 2 and 6 weeks of treatment.
- ESS clinical response, defined as $ESS \leq 10$ after 2 and 6 weeks of treatment.
- ESS clinical response, defined as either $ESS \leq 10$ after 2 and 6 weeks of treatment or ESS absolute decrease from baseline of at least 3.0 points after 2 and 6 weeks of treatment.

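### PSG/MWT participation stratifies the randomisation but is absent from the primary ANCOVA and the other efficacy models; adding it is a small, nearly free improvement

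*SAP*

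**What the plan says.** **Randomisation.** Protocol 8.6.6: "The randomisation will be stratified by region and by the polysomnography and the MWT assessment", with about half of subjects in the PSG/MWT subset. Participation is recorded first and then determines which number the subject receives. Protocol 11.3 aims for 1:1:1:1 among those who do and those who do not have the assessment, and says "a down-up/up-down strategy will be followed in order to simplify the stratified randomisation". Footnote 11 of the schedule (Protocol 18.15) says the PSG/MWT subjects are "all recruited in sites with sleep units available".

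**Analysis.**
- Primary ANCOVA, SAP 10.1: "ANCOVA model, with the baseline ESS as a covariate, region and treatment as a factor". Protocol 11.1.4 has the same terms: "with the baseline ESS as a covariate, region and treatment as a factor".
- MMRM, SAP 10.1.2: treatment, region, visit, treatment-by-visit and baseline ESS.
- Rank ANCOVA, SAP 10.1.4: modelled on the primary analysis.
- MCP-Mod, SAP 10.1.3: "dose as fixed factor and baseline ESS as covariate", so neither stratification factor appears.
- Secondary ANCOVAs, SAP 10.2: "considering baseline corresponding endpoint evaluation as covariate and treatment and region as fixed factors". The responder logistic models have the same structure.

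Neither document explains why the PSG/MWT stratum is left out, or says whether it predicts ESS change.

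**The concern.** A model normally includes the factors used to stratify the randomisation. Stratifying removes between-stratum variation from the treatment comparison, but a model without the factor leaves that variation in the residual. The reported standard error is then larger than the true one, so the test falls below its nominal level and some power is lost. If the strata end up unbalanced between arms, the resulting shift stays in the estimate. It averages zero over randomisations, but adjustment would remove it from the trial actually run.

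The plan treats its two strata differently: region is both stratified and modelled, PSG/MWT is stratified only. Because PSG/MWT subjects come from sites with sleep units, the stratum follows site type. Some relation to ESS change is therefore plausible, though nothing in the documents shows one.

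**Working it through.** **Inputs from the documents.** Effect 3.0 points, SD 5.0, two-sided alpha 0.05, 50 completed per arm in four arms (SAP 5); three regions (Protocol 11.3); about half of subjects in PSG/MWT (Protocol 8.6.6).

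**Assumptions.** Stratum difference in ESS change, *g*: 0 to 3 points, where 3 is the trial's whole target effect. Strata split 50/50. Baseline ESS taken as uninformative.

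**The plan's own figure.** Effect 3.0, SD 5.0 and 80% power need 45 per group by two-sample t-test, not 50. At 50 per group the power is 84.4%. The stated 50 is reached at SD 5.3, the top of the range in Protocol 7.2. That is a separate matter; it means the starting point here is a little above 80%.

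**Degrees of freedom.** The planned model has 200 − 7 = 193 residual df (intercept, three treatment, one baseline, two region). With the factor it has 192. The critical t moves from 1.9723 to 1.9724.

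**Balanced strata, within-stratum SD 5.** The true SE of one dose-placebo contrast is 5 × √(2/50) = 1.0. Without the factor, the residual SD is √(25 + g²/4), so the effective critical value is 1.9723 × √(25 + g²/4)/5. Power and type I error are tail areas of the t distribution (193 df) beyond that value, with noncentrality 3 and 0 respectively.

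| g | residual SD without | critical value | power without | power with | type I without | type I with |
|---|---|---|---|---|---|---|
| 0 | 5.00 | 1.972 | 84.7% | 84.7% | 5.0% | 5.0% |
| 1 | 5.02 | 1.982 | 84.5% | 84.7% | 4.9% | 5.0% |
| 2 | 5.10 | 2.011 | 83.8% | 84.7% | 4.6% | 5.0% |
| 3 | 5.22 | 2.059 | 82.6% | 84.7% | 4.1% | 5.0% |

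Simulation (20,000 trials per setting) agrees within about 0.3 percentage points.

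**Alternative reading: total SD fixed at 5.** The within-stratum variance is then 25 − g²/4.

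| g | power without | power with | 95% CI half-width without | with |
|---|---|---|---|---|
| 0 | 84.7% | 84.7% | 1.972 | 1.972 |
| 1 | 84.9% | 85.1% | 1.972 | 1.963 |
| 2 | 85.2% | 86.1% | 1.972 | 1.933 |
| 3 | 85.9% | 87.9% | 1.972 | 1.882 |

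Type I error without the factor is 5.0%, 4.9%, 4.6% and 4.0%. The gain is 0 to about 2 points of power on either reading.

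**Chance imbalance.** The shift in one contrast is *g* times the absolute difference in PSG/MWT share between that dose arm and placebo. It depends on block size and on how numbers reach sites, which the documents do not fix. Simulated allocations (230 subjects, 48 sites, half PSG/MWT) at g = 2 give, as mean / 95th percentile in ESS points:

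| Supply mechanics (assumed) | blocks of 4 | blocks of 8 |
|---|---|---|
| each site has both kinds of subject | 0.15 / 0.36 | 0.15 / 0.37 |
| PSG/MWT is an attribute of the site | 0.06 / 0.15 | 0.09 / 0.22 |
| both ends drawn from a regional list | 0.02 / 0.05 | 0.03 / 0.07 |

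At g = 1 these halve. All are small against the SE of 1.0.

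**The case against.** **No demonstrated harm.** Nothing shows that the stratum is prognostic, and at 0 or 1 point the power gain is 0.0 or 0.2 percentage points. A 3-point difference would make a marker of site logistics as strong as the target drug effect. This stands, and it is why the point is minor.

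**The stratum may be purely operational.** It may exist only to keep arms balanced in the subset sized for the MWT (at least 20 per group, SAP 5). That is a fair inference, but the documents do not say so. It would explain the stratification without being a reason to ignore the factor in whole-sample models.

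**The apparent power loss depends on the SD convention.** Correct: with total SD fixed at 5, power does not fall below 84.7%, and the factor only adds headroom. Power exceeds 80% on both readings. The gain from adding the factor is much the same either way.

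**Chance imbalance is ordinary sampling variability.** This also stands. In simulations where the strata were left unbalanced, type I error without the factor stayed near 5%; adding it still gained up to about 2.5 points of power at g = 3.

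**The pooling rule may absorb the factor.** SAP 10.4.1 gives any site with at least 20 subjects its own category. But 230/48 is about 5 subjects per site, so few sites would qualify even if recruitment is uneven.

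**MCP-Mod's omission of region is a different issue.** True. It is mentioned because the same edit repairs it.

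**Conclusion.** The omission is real and unexplained, and its consequence is small. Leaving the factor out causes no bias and no type I inflation. If the strata differ in ESS change, the test is slightly conservative: it gives up at most about 2 points of power, and type I error falls to about 4%, at a 3-point difference. At 1 point or less the loss is negligible. It is certain that the factor is missing from the models. The size of the effect is uncertain, because the stratum difference, block size and supply mechanics are all assumed. This is a minor point, worth acting on because the remedy costs almost nothing.

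**What to change.** - Add PSG/MWT participation (yes/no, as recorded at randomisation) as a fixed factor in the primary ANCOVA.
- Enter it before treatment. SAP 10.1 says the overall treatment test "will be decomposed using Type I sums of squares into three orthogonal single DF contrasts", and sequential sums of squares adjust treatment only for terms that precede it.
- Add it to the jump-to-reference imputation model (SAP 9.1 and 10.4.2), the MMRM, the rank ANCOVA, MCP-Mod and the secondary ANCOVAs. Exclude endpoints measured only in the PSG/MWT subset, where the factor is constant.
- Add region to MCP-Mod.
- In the responder logistic models the factor is optional, since it changes the conditional odds ratio being estimated.
- Otherwise, state why the stratum is left out.

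The cost is one degree of freedom and one term per model. No new data are needed, because participation is recorded before randomisation. The change should be made before unblinding so that it cannot be read as data-driven.
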